3.6.5.2 Discharge destination

Destination at hospital discharge will be specified using the following categories:

- Home
- Home with nursing care
- Transfer to another hospital
- Rehabilitation centre
- Nursing home or other long-term care facility
- Other
- No information

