2.3 Exploratory objectives

- 4 To calculate pathogen-specific SARI incidences and describe trends in hospitalised adults (time period, country, level of severity);
- 5. To perform feasibility assessments for future respiratory disease studies within the id.DRIVE Study Network (e.g., effectiveness studies, impact studies).

² Healthcare utilisation outcomes are defined by outcome (hospitalisation without ICU admission or in-hospital death; ICU admission without in-hospital death; in-hospital death), by the need for respiratory support (none; non-invasive ventilation; mechanical ventilation; ECMO), discharge destination and length of stay.

Confidential

¹ SARS-CoV-2 and/or SARS-CoV-2 specific variant, Influenza A/B, Respiratory Syncytial Virus (RSV) A/B, Adenovirus, Parainfluenza viruses (1-4), human metapneumovirus (hMPV), human rhinovirus (HRV), human enterovirus (HEV), human coronaviruses (229E/NL63/OC43/HKU1)

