3.6.6 Risk groups

Risk groups will consist of those patients with specific chronic conditions (e.g., immunocompromised), long-term care facility residents, and the elderly. A specific categorisation of risk groups will be provided in the SAP.

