Time between symp	tom	Days, continuous
onset and hospitalis	ation	
Long-term care facili	ty	Binary, if no, specification of residential situation before
residence [§]		hospitalisation: Home, Home with nursing care, Transfer from
		another hospital, Rehabilitation centre, Nursing home, other,
		no information
Respiratory support		None, oxygen therapy, non-invasive ventilation, mechanical
		ventilation, extra corporeal membrane oxygenation (ECMO),
		other
Cumulative number	of days of	Days, continuous
non-invasive ventila	tion,	
invasive ventilation,	or ECMO	
Length of hospital st	ау	Days, continuous
Admission to ICU		Binary
Length of ICU stay		Days, continuous
In-hospital death		Binary

Covariate	Description
Post-discharge destination	Home, Home with nursing care, Transfer to another hospital,
	Rehabilitation centre, Nursing home or other long-term care
	facility, Other
Treatments received during	Antibiotics, Antiviral drug(s), Corticosteroid(s), Immune-
hospital stay for the	modulator(s), Anti-SARS-CoV-2 antibodies, Other monoclonal
management of SARI episode	antibodies, None of the above.
	Brand name if anti-SARS-CoV-2 antibodies received during
	hospital stay
Treatments received prior to	Antibiotics, Antiviral drug(s), Corticosteroid(s), Immune-
hospital admission for the	modulator(s), Anti-SARS-CoV-2 antibodies, Other monoclonal
management of current SARI	antibodies, None of the above.
episode	Brand name if anti-SARS-CoV-2 antibodies received during
	hospital stay
Medicinal product for the	Binary. If yes, type (Antiviral drug,
prevention of SARS-CoV-2	Anti-SARS-CoV-2 antibodies, Other), brand and date
(pre- or post-exposure	(month/year) if SARS-CoV-2 monoclonal antibody
prophylaxis) in the 12 months	
prior to current	
hospitalisation	
Medicinal products for the	Binary. If yes, type (Antiviral drug,
prevention of RSV infection	Anti-RSV antibodies, Other), brand and date (month/year) if
within 12 months prior to	RSV monoclonal antibody
current hospitalisation	

*Definitions for each chronic conditions are specified in the id.DRIVE Common dataset case report form

§ At VAHNSI, long-term care facility residents are excluded

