3.13.3 Demographic and clinical characteristics of SARI

Demographic and clinical characteristics of the SARI patients will be provided, overall and by SARIcausing pathogen (type and/or subtype), including age groups, gender, symptoms, presence of chronic conditions, BMI, vaccination status, having had preventive monoclonal antibodies, pregnancy, smoking history, use of antiviral or virus-specific monoclonal antibody therapy, long-term care facility residence, and healthcare utilisation outcomes. Overall clinical characteristics will also be provided stratified by calendar month of disease-onset.

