3.13.4 Healthcare utilisation outcomes

Multinomial logistic regression will be used to explore risk factors of pathogen-specific SARI hospitalisation, healthcare utilisation outcomes (as defined in Section 3.6.5), and the presence of co-infections (by number of co-infections and involved pathogens, when feasible). Potential risk factors include age, gender, chronic conditions, smoking). Stratified analyses will be performed by age groups, by gender, by presence of chronic condition and specifically by those with pre-existing immunodeficiency disorders.

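### Discharge destination is defined without pre-admission residence, so comparisons by pathogen or co-infection are confounded by where patients already lived

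*Protocol*

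**What the plan says.** **Outcome.** The footnote to the objectives in Protocol section 2 ends its list of healthcare utilisation outcomes with "ECMO), discharge destination and length of stay". Objective 2 characterises patients by pathogen, including these outcomes. Objective 3 asks about the impact of co-infection on them.

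**Definition.** Section 3.6.5.2 reads "Destination at hospital discharge will be specified using the following categories" and lists seven categories. One is "Nursing home or other long-term care facility"; another is home with nursing care. None refers to where the patient lived before, and none is ranked.

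**Baseline data.** Table 3 (section 3.9) records long-term care facility (LTCF) residence as "Binary, if no, specification of residential situation before" admission. The sub-answers include home, home with nursing care, transfer from another hospital, rehabilitation centre and nursing home. A footnote states that LTCF residents are excluded at VAHNSI.

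**Analysis.** Section 3.13.2 describes co-infections by healthcare utilisation outcome. Section 3.13.3 lists, overall and by pathogen, "use of antiviral or virus-specific monoclonal antibody therapy, long-term care facility residence, and healthcare utilisation outcomes". Section 3.13.4 states "Multinomial logistic regression will be used to explore risk factors of pathogen-specific SARI hospitalisation, healthcare utilisation outcomes", the outcomes being taken as defined in 3.6.5. It continues "Potential risk factors include age, gender, chronic conditions, smoking". The strata it names are age group, gender, chronic condition and immunodeficiency. Section 3.6.6 includes "long-term care facility residents, and the elderly" among the risk groups and leaves their categorisation to the SAP.

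**The concern.** Where a patient goes on discharge depends heavily on where the patient came from. A person who lived in a nursing home will usually return there whatever virus caused the admission. When the outcome is destination alone, a pathogen or co-infection group with more prior residents shows more facility discharge even if no patient in either group has changed level of care. The same applies to home with nursing care, which merges existing and new care.

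Objective 3 asks about impact, so the reader will want to attribute differences in destination to the co-infection. The planned definition does not allow that, because part of any difference is the baseline living situation carried through the admission. The model in 3.13.4 has a related problem: age and chronic conditions plausibly go with prior residence, so their associations with destination partly reflect it too.

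**Working it through.** The plan states no figure on this point, so there is none to reproduce. The check sets the sections side by side and then illustrates the mechanism.

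**1. Does any planned analysis link destination to prior residence?**
- Definition (3.6.5.2): no.
- Named model factors (3.13.4): age, gender, chronic conditions, smoking. No.
- Named strata (3.13.4): age, gender, chronic condition, immunodeficiency. No.
- Risk-group breakdown (3.13.2): stated for counts and proportions positive, not for destination.
- Table by pathogen (3.13.3): LTCF residence and the utilisation outcomes both appear, but as separate marginal distributions. Two marginal tables cannot show who changed level of care; that needs the two variables cross-classified within patients.

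**2. Do the before and after categories match?** No. Before admission, nursing home is a sub-answer reached only when LTCF residence is *no*. At discharge, nursing home and LTCF are one category. A nursing-home resident may thus be coded LTCF = no, and adjusting for that flag alone would miss such patients.

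**3. Illustration.** All inputs here are assumed; the protocol gives none of them. Among patients discharged alive, let r be the share who lived in a facility before admission, s the share of those who return to one, and q the share of the others who are newly placed. With s and q the same for every pathogen:

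P(facility discharge) = r·s + (1 − r)·q

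Difference between groups A and B = (r_B − r_A)·(s − q)

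Take s = 0.95 and q = 0.04:
- r = 0.05: 0.0475 + 0.0380 = 0.0855, about 8.6%
- r = 0.10: 0.0950 + 0.0360 = 0.1310, or 13.1%
- r = 0.15: 0.1425 + 0.0340 = 0.1765, about 17.7%

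For 5% against 15% residents the difference is 0.10 × 0.91 = 9.1 points and the ratio 0.1765/0.0855 = 2.1. For 5% against 10% the ratio is 0.1310/0.0855 = 1.5. With equal r the difference is zero. Among patients not previously in a facility, the rate is 4% in both groups.

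**4. Sensitivity to the assumptions.** With s = 1 and q = 0.05, shares of 5% and 15% give 9.75% and 19.25%, a crude odds ratio of 2.21; among non-residents the odds ratio is 1.00. With r = 5% against 10% to 25% and q from 3% to 10%, the crude odds ratio runs from 1.38 to 4.40.

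**5. Does age adjustment remove it?** Only in part. The formula holds within an age group, with r now the resident share in that group. Adjustment removes the part of r_B − r_A that age explains; differences in residence between patients of the same age remain.

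**6. Sites.** VAHNSI has 5 of the 22 hospitals (5/22 = 23%; 5 × 300 = 1,500 of the 6,600 planned patients). Its excluded residents cannot contribute to the distortion there, but the destination mix then differs between sites by design.

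**The case against.** The strongest case on the other side has four parts.

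*The protocol does not treat nursing-home discharge as a bad outcome.* This stands. A reader might infer that returning residents are scored as failures, but the categories are unranked, the model is multinomial and so treats them as nominal, and severity is defined separately through ICU admission, death and respiratory support. The confounding does not depend on any ranking.

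*Prior residence is not ignored.* This also stands for the study as a whole: it is collected, LTCF residence is reported by pathogen, and LTCF residents are a risk group. It is not, however, linked to the outcome, and reporting both margins does not supply that link.

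*The factor list is open, the model is exploratory, and the SAP specifies the analyses.* It is true that the list is introduced with *include*, and that the SAP, which is not among the documents reviewed, could add residence. But the outcome definition is fixed in the protocol and 3.13.4 points back to it; section 3.6.6 leaves only the categorisation of risk groups to the SAP. A definition that merges two different events is more than an omitted detail.

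*Actual destination is legitimate description.* Agreed for characterising patients under objective 2, and the raw table should stay. It does not suffice for comparing pathogens or for the impact question in objective 3.

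**Conclusion.** The point holds in a limited form. The definition in 3.6.5.2 merges return to an existing placement with new placement, and neither the factors nor the strata named in 3.13.4 include prior residence. Comparisons of destination by pathogen or co-infection are therefore confounded by baseline living situation, and age accounts for only part of this.

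The size cannot be derived from the protocol, which gives no resident share by pathogen, no return rate and no rate of new placement. The 8.6% against 17.7% is an illustration: it follows from choosing a threefold difference in resident share and disappears when the shares are equal. A reader might take a doubling as the expected bias, but the document does not support that. Nor does it support reading the plan as counting facility discharge against a pathogen.

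The point concerns one of several utilisation outcomes, in descriptive and exploratory analyses. It is worth correcting because the correction is cheap; it does not touch the positivity estimates of objective 1.

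**What to change.** Keep the raw destination table in 3.6.5.2 as description. For the pathogen and co-infection comparisons and the 3.13.4 model, add a derived outcome that uses the residence data in Table 3. One form is new institutional placement among patients discharged alive who were not in a facility before admission, with new home nursing care defined in the same way among patients not already at that level of care. At the least, name prior residence in 3.13.4 as a stratum or adjustment factor for destination.

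State the mapping explicitly:
- Combine LTCF residence = yes with the sub-answer nursing home into one prior-facility category, to match the merged discharge category.
- Treat transfer from another hospital and no information as unknown prior residence, and report how many patients this affects.
- Note beside the results that LTCF residents are excluded at VAHNSI, so destination mixes are not directly comparable across contributors.

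Cost: no new data collection. There is a small mapping step, and some patients will have unclassifiable prior residence and drop out of the derived outcome.

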3.6.5.3 Length of stay

Length of stay is defined as the number of days between date of admission and date of discharge or in-hospital death.

Length of ICU stay is defined as the number of days between date of admission to the ICU and date of discharge from ICU or in-hospital death.

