2.2 Secondary objectives

3 To investigate the prevalence of co-infection with the viral respiratory pathogens of interest¹, in adult patients hospitalised with SARI, and the impact on healthcare utilisation outcomes².

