3.5 Study outcomes

The outcome of interest for the primary objectives will be **laboratory-confirmed infection** (Section 3.6.3) with one of the viral respiratory pathogens of interest (see section 3.8.1) in patients hospitalised with SARI symptoms, and laboratory-confirmed co-infection (section 3.6.4) for the secondary objective.

For the second secondary objectives, healthcare utilisation outcomes of interest are:

- Level of severity (Section 3.6.5.1).
- Discharge destination (Section 3.6.5.2)
- Length of stay (section 3.6.5.3)

Pathogen-specific SARI incidences will be calculated to address the first exploratory objective (see section 3.13.5). The denominator will be based on the sum of the catchment populations covered by the Study Contributors [26].

For the second exploratory objective, **feasibility assessments** for future respiratory disease impact and effectiveness studies will be made as described in Section 3.13.6.

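### Length of stay ends at discharge or in-hospital death alike, so mortality differences can distort comparisons in either direction; separately, 3.13.4 names a categorical model for a stay recorded in continuous days

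*Protocol*

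**What the plan says.** Protocol 3.6.5.3 fixes the outcome: "Length of stay is defined as the number of days between date of admission and date of discharge or in-hospital death". ICU stay has the same construction, the "number of days between date of admission to the ICU and date of discharge from ICU or in-hospital death". No section separates the two kinds of ending when length of stay is reported.

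Length of stay is a healthcare utilisation outcome in Section 3.5 and in the footnote to the objectives in Section 2. Primary objective 2 characterises patients on these outcomes, overall and by pathogen. Secondary objective 3 concerns co-infection and "the impact on healthcare utilisation outcomes". Sections 3.13.2 and 3.13.3 describe co-infections and pathogens by these outcomes.

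For modelling, 3.13.4 says: "Multinomial logistic regression will be used to explore risk factors of pathogen-specific SARI hospitalisation, healthcare utilisation outcomes (as defined in Section 3.6.5". Section 3.6.5 contains four kinds of outcome: ICU/death severity, respiratory support, discharge destination and length of stay. Table 3 (Section 3.9) records hospital stay and ICU stay in days on a continuous scale and gives no categories.

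Two other provisions matter. In-hospital death is a severity category of its own in 3.6.5.1, subdivided into deaths during and outside the ICU stay. Section 3.13 leaves the full set of analyses to the SAP, which is not shown.

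**The concern.** A patient who goes home on day 4 and a patient who dies on day 4 both contribute a stay of 4 days. In-hospital death prevents discharge alive, so it is a competing event, and the pooled variable puts opposite outcomes on one scale. If two pathogens, or single infection and co-infection, differ in mortality, their stays can differ, or fail to differ, for reasons unrelated to speed of recovery. A reader of objective 3 could then draw a wrong conclusion about the impact of co-infection. ICU stay carries the same ambiguity.

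The second problem is one of fit. A multinomial logistic model needs an outcome in categories. Read literally, 3.13.4 applies it to a number of days.

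**Working it through.** **Figures in the plan.** The protocol gives no mortality, no mean stay and no time to death. Its only sample-size figures are the patient number (300 × 22 × 0.90 = 5,940, which reproduces) and the Table 4 precision for prevalence. Neither bears on length of stay, so the inputs below are assumptions chosen to show a range.

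**Check 1: mixture of survivors and deaths.** Let m be in-hospital mortality, S the mean stay of patients discharged alive and D the mean time to death.

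Pooled mean stay = (1 - m) × S + m × D

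With S = 10 days in every group, and m = 0.05 against m = 0.20:

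| Deaths at day | m = 0.05 | m = 0.20 | Change |
|---|---|---|---|
| 5 | 9.5 + 0.25 = 9.75 | 8 + 1 = 9.00 | -0.75 |
| 10 | 9.5 + 0.50 = 10.00 | 8 + 2 = 10.00 | 0 |
| 15 | 9.5 + 0.75 = 10.25 | 8 + 3 = 11.00 | +0.75 |

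The change equals (0.20 - 0.05) × (D - 10). Its sign depends only on whether deaths come before or after the typical live discharge.

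**Check 2: constant competing hazards.** Let d be the daily hazard of live discharge and h that of death. Then m = h/(d + h), and mean stay = 1/(d + h) = (1 - m)/d.

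- d = 0.10, m = 0.05: 0.95/0.10 = 9.5 days
- d = 0.10, m = 0.10: 0.90/0.10 = 9.0 days
- d = 0.10, m = 0.20: 0.80/0.10 = 8.0 days
- d = 0.08, m = 0.20: 0.80/0.08 = 10.0 days
- d = 0.07, m = 0.20: 0.80/0.07 = 11.4 days

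In the first three rows the discharge hazard is the same, yet stay falls by 1.5 days as mortality rises from 5% to 20%. In the last two rows the deadlier group is also discharged more slowly, and its stay is longer than 9.5 days.

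**Check 3: would splitting by vital status be enough?** With constant hazards, the timing of the end of stay is the same for deaths and live discharges. Mean stay among patients discharged alive is therefore also 9.5 and 8.0 days at d = 0.10 and m = 0.05 and 0.20. The split is informative but does not by itself make a fair comparison.

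The cumulative incidence of live discharge by day t is (1 - m) × [1 - exp(-(d + h)t)]. At day 10:

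- m = 0.05, d + h = 0.10/0.95 = 0.1053: 0.95 × (1 - 0.349) = 61.8%
- m = 0.20, d + h = 0.10/0.80 = 0.125: 0.80 × (1 - 0.2865) = 57.1%

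The deadlier group has the shorter mean stay but the lower probability of having left alive. The second quantity is the one a reader needs.

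**Check 4: model against variable.** The severity categories, respiratory support and discharge destination are all categorical and can go into a multinomial model. Length of stay is continuous in Table 3, and no section gives cut-points. Sections 3.13.4 and 3.9 do not fit as written.

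**The case against.** The strongest reply is that the definition suits its label. Length of stay is a utilisation outcome, and a patient who dies on day 4 did use four days of care. In-hospital death is reported beside it in 3.6.5.1, so a mortality difference is not hidden. This stands: the pooled figure is a valid count of bed-days used. It does not make that figure interpretable as recovery time or care need when groups with different mortality are compared.

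The next reply is that analysis detail belongs in the SAP. No section prescribes a pooled mean or a test of length of stay, 3.13.4 only explores, and the SAP could categorise stay just as it groups age. This stands in part. A multinomial model could be fitted to a categorised stay, so it would be too strong to say that the model cannot be used. But the protocol itself fixes both the definition and the model, and categories of the pooled variable would still place early deaths with early recoveries.

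The remedy also has limits. Stay among patients discharged alive conditions on survival and leaves out the days used by those who died. Censoring transfers would assume that transfer is unrelated to prognosis. Both are reasons to retain the pooled figure and to show transfers separately.

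A reader might go further and infer that a deadlier pathogen or co-infection will appear to need less hospital care. Inputs can be chosen to give that result. With deaths at day 4, survivors at 10 days and 25% mortality, the mean is 0.25 × 4 + 0.75 × 10 = 8.5 days. A group with survivors at 9 days and 5% mortality has 0.05 × 4 + 0.95 × 9 = 8.75 days. The protocol offers no data to support those inputs, and later deaths or slower discharge give the opposite. Its own background section cites a cohort study in which RSV, with morbidity described as comparable to or more severe than influenza, had the longer stays.

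**Conclusion.** The point holds in a limited form. Hospital and ICU length of stay pool two opposite endings, so comparisons by pathogen or co-infection can be distorted by mortality in either direction. The assumed range is -0.75 to +0.75 days for mortality of 5% against 20%, a survivor mean of 10 days and deaths at day 5 to 15. With constant hazards and an unchanged discharge rate, the shift is -1.5 days. All of these inputs are assumptions, and the true size and sign cannot be known from the protocol.

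The mismatch between the multinomial model in 3.13.4 and the continuous variable in Table 3 rests on the text alone. It is a wording fault that is easily repaired. The documents do not support a claim that severe infections will look less demanding, or that the named model could never be applied to length of stay.

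**What to change.** - In 3.6.5.3, keep the pooled hospital and ICU figures and label them as bed-days used.
- Add hospital stay separately for patients discharged alive and patients who died. Split ICU stay in the same way.
- Compare pathogen and co-infection groups by the cumulative incidence of live discharge, with in-hospital death as competing event. Show transfers to another hospital as a separate category.
- In 3.13.4, limit multinomial logistic regression to severity, respiratory support and discharge destination, and name the method used for length of stay.

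The cost is a few sentences in the protocol and somewhat more analysis. Admission and discharge dates, in-hospital death, ICU stay and discharge destination are already collected, so no new data are needed.
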